5. Minorities and Women: Because the VA population is largely male, the proportion of females enrolled will not be representative of actual prevalence rates. Although most recruitment will occur in mental health clinics, recruitment within women’s health clinics will be used to try to maximize the enrollment of eligible women. Ethnic and racial minorities are well-represented in the VA population and study staff will be trained to recognize the variations in symptom presentation characteristic of ethnic and racial minorities so that potential participants from these groups will not be excluded.

B. Screening Assessments

Patients who are screened for possible eligibility for the study will be listed on the Patient Screening Log. After the patient signs the Informed Consent Form, the screening procedures and assessments can be initiated. A template of the Informed Consent Form can be found in Appendix A. The screening phase will last between two and four weeks to allow adequate time for all of the assessments to be completed, to assure the patient's capacity and willingness to participate in the study and to ensure that all patients have HRSD24 scores above entry criteria for the study within seven days prior to randomization. If the SI feels that the patient may not be capable of giving informed consent, the SI may request a competency evaluation using the VA standard clinical protocol. All assessments and their frequencies of administration are listed in Table 2 in Protocol section VI.G. Although screening data will not be used in the primary analysis, it will be retained to determine if participants who entered the study were comparable to those who were excluded.

C. Randomization to Treatment

Patients who sign the Informed Consent Form and meet the study eligibility criteria will be enrolled into the study and will be randomized into one of 2 treatment groups: rTMS or sham rTMS. Patients who fail screening may be re-screened at a later time at the discretion of the site investigator.

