The CSP Clinical Research Pharmacy Coordinating Center (CSPCRPCC or PCC) will be responsible for initially evaluating all serious adverse events for patient safety concerns and will confer with the Study Chair (or another physician member of the Executive Committee if the Study Chair is unavailable) as required during this evaluation process. After being reviewed by the Study Chair, the PCC Director and the CSPCC Director, any event deemed to be related, serious and unexpected will be reported to CRADO, study investigators, and FDA.

Expedited Reporting by sites to the Study Sponsor (CSP): All Serious Adverse Events (SAEs) which includes Unanticipated Adverse Device Effects (UADEs) require prompt reporting, within 72 hours of the site investigator being made aware of the event. The SAE reports will be forwarded within 72 hours of discovery of an SAE by the study site to Perry Point CSPCC who will immediately notify the CSPCRPCC and the Chairman’s Office. If the SAE is not resolved at the time the event is reported, the site must monitor and provide SAE follow-up information at least every 30 days until the SAE becomes resolved. The site must handle requests for SAE Follow-up information in the same prompt manner that the original SAE reports are handled

Expedited Reporting by the Sponsor to the FDA: The Chairman and Study Pharmacist will review the SAE report to assess completeness of documentation and to determine whether the SAE requires expedited reporting to the FDA.

Specifically, if an event meets the criteria for unexpectedness (i.e., not previously reported), seriousness (by definitions in section H.2.), and relatedness, it will be reported to the FDA within 10 working days for UADEs and within 7 calendar days for unexpected SAEs (Safety Reports) of the sponsor (Cooperative Studies Program) receiving the report as required by regulation.

4. Data Monitoring Committee (DMC) Reporting of Adverse Events, Adverse Device Effects, Serious Adverse Events, and Unanticipated Adverse Device Effects. The Clinical Research Pharmacist and the Study Biostatistician will generate tabulations of AEs and SAEs and present a summary of these to the DMC on a schedule set by the DMC. The DMC will also determine when they should be unblinded to treatment assignment for the reviewing of adverse event data. The DMC will advise the CSP Director concerning whether the study should continue or be stopped for safety reasons.

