modified or terminated. The DMC can consider patient safety or other circumstances as grounds for early termination, including either compelling internal or external evidence of treatment differences or infeasibility of addressing the study hypotheses (e.g., poor patient intake, poor adherence to the protocol). The DMC will meet annually to review data reports prepared by the CSPCC. At the six-month interval between the annual meetings, the DMC will receive a data report for their review. Any member of the DMC can ask for a meeting of the group if he/she feels that it is necessary, based upon the data. This group will receive outcome data during the course of the study.

In order for the DMC to make its recommendation for continuation of the study, it will be necessary for them to see the analyses for the primary outcome measure every time that the report is run and it is possible to calculate the primary outcome measure. Periodic monitoring of interim results can significantly affect the probability of making an incorrect decision. A number of formal techniques have been developed for interpreting interim results. At the organizational meeting, the DMC will select the technique that it wants to use to monitor the study. Suggested techniques are the Haybittle-Peto and Lan-DeMets group sequential boundaries. For the Haybittle-Peto method, a constant z-statistic is used as the monitoring boundary. The Lan-DeMets procedure produces decision boundaries that are quite conservative over the first several looks and then gradually converges to the nominal alpha levels as the final look is approached. Figure 3 gives an example of the Lan-DeMets boundaries for five looks at an alpha level of 0.05.

Figure 3. Lan De - Mets Group Sequential Monitoring Boundaries

4. Human Rights Committee (HRC)

The Human Rights Committee (HRC) will conduct annual site visits to ensure that patients' rights and safety are being properly protected.

5. Internal Reviews

The Study Chairman, the Study Biostatistician, the CRP and the CSPCC Project Manager will communicate regularly and frequently to review study status. Discussion items will include overall and site-specific enrollment, regulatory issues, protocol compliance and data completeness and quality. Action plans to deal with identified problems will be developed.

6. Site Monitoring, Auditing and Resource Team (SMART)

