If after 100 patients are enrolled 3% of the total enrolled participants have a completed suicide or 6% have attempted suicide, enrollment will be suspended pending an analysis of the SAE data by the DMC. The DMC will review all reports of suicides and suicide attempts carefully to determine whether suicide risks are excessive. If so, recommendations for restart of study enrollment may entail modifications to procedures which would be subject to IRB and FDA approval. If risk of suicide is not deemed excessive, the study will be restarted without modifications. All suicide attempts and completions will be considered SAEs, and as such, will be reported to the study executive committee, Central IRB, and the DMC by the Clinical Research Pharmacist and Study Biostatistician. The DMC will monitor all SAEs regularly (at least every 6 months) throughout the study and assess potential for increased risks to patients. The DMC may also impose requirements for more frequent monitoring of SAEs. We recognize that study termination or modification based on serious adverse events, such as suicide attempts, ultimately rests with the DMC, the Central IRB, and the study

executive committee and that more stringent stopping points may be initiated during the study.

9. Special Procedures for the Monitoring of Seizures

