An independent oversight committee called the Data Monitoring Committee (DMC) will monitor study progress. This committee meets on the same basic schedule as the Study Group and Executive Committee, i.e., they will meet at 6 to 9 months after the start of patient recruitment and yearly thereafter. Initially, they will meet once prior to the study start-up to acquaint themselves with the study and to establish monitoring guidelines. This committee does not usually meet during the last six months of a study.

[figure not shown]
The major responsibility for the DMC members when they meet is to make a recommendation to the Director of the Cooperative Studies Program on whether the study should continue or not. The study could be recommended for termination due to poor recruitment, treatment differences so large that it is possible to reach a final decision, treatment differences so small that continuation would be irresponsible. The

DMC also reviews the participating sites' performance and makes recommendations on them. Their final responsibility is to review all proposed protocol changes and subprotocols and to make recommendations as to their acceptability.

In order for the DMC to carry out its responsibilities, the CSPCC Study Team will provide the committee with a report approximately three weeks prior to their meetings. The report will consist of the tables described previously for the Study Group and Executive Committee reports as well as those presenting outcome analyses. It is the responsibility of the CSPCC Study Team to provide the DMC with whatever information the Board feels that it needs to successfully monitor the study. Thus, additional tables will be added as required. In addition to the reports for the yearly meetings, the DMC will also be provided with reports between meetings at 6-month intervals.

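### The automatic suicide suspension rule starts only at 100 enrolled patients, so its own counts, if reached earlier, trigger no mandatory pause

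*Protocol*

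**What the plan says.** Section X.B.8 (safety of potentially suicidal or dangerous patients) states: "If after 100 patients are enrolled 3% of the total enrolled participants have a completed suicide or 6% have attempted suicide, enrollment will be suspended". The suspension lasts until the DMC has analysed the serious adverse event (SAE) data, and enrolment may restart with or without changes.

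Other provisions apply from the first patient:
- Appendix D, section V, on the DMC before the study starts: "Initially, they will meet once prior to the study start-up to acquaint themselves with the study and to establish monitoring guidelines". After that, "they will meet at 6 to 9 months after the start of patient recruitment and yearly thereafter".
- Section X.B.8: "The DMC will monitor all SAEs regularly (at least every 6 months) throughout the study". It adds that "more stringent stopping points may be initiated during the study".
- Section VI.H.3: SAEs "require prompt reporting, within 72 hours of the site investigator being made aware of the event". Suicides and suicide attempts count as SAEs.
- Section X.B.3: "Any member of the DMC can ask for a meeting of the group if he/she feels that it is necessary".

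The neighbouring seizure rule in X.B.9 suspends enrolment at a fixed count of 10 participants, with no minimum number enrolled.

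The word *enrolled* has two meanings. Section VI.C says: "Patients who sign the Informed Consent Form and meet the study eligibility criteria will be enrolled into the study and will be randomized". Section VI.A.3 uses it for the 720–800 patients expected to consent.

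**The concern.** The sponsor has judged that 3 suicides or 6 attempters among 100 patients are enough to require a pause. Counts of affected participants cannot fall, so the same counts among 50 or 75 patients are stronger evidence of a problem. As written, they suspend nothing automatically.

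A minimum denominator is a sensible guard for a percentage rule, because 1 suicide among 33 patients already exceeds 3%. It does not explain why the fixed counts of 3 and 6 are withheld, since these cannot fire on one or two events. At stake is whether more patients are randomised between the moment the sponsor's own alarm count is reached and the moment someone decides to act.

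**Working it through.** **The rule's own figures.** 3% × 100 = 3 and 6% × 100 = 6. Reached earlier, the same counts correspond to these rates:
- 50 patients: 3/50 = 6% and 6/50 = 12%
- 75 patients: 3/75 = 4% and 6/75 = 8%

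**When patient 100 enters.** Appendix D, section IV.A plans 1.1–1.5 patients per site per month, and there are 9 sites, so 9.9–13.5 per month. 100/9.9 = 10.1 months; 100/13.5 = 7.4 months.

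**How often the counts come early.** The protocol gives no event risks, so these are assumptions: half, one and two times the rule's own levels, with first events spread evenly over 7 months per participant. Section VI.D implies 28–35 weeks from the start of treatment, and 28 × 12/52 = 6.5 months to 35 × 12/52 = 8.1 months. Entry is at a constant rate and *enrolled* is read as randomised. Results are from 100,000 simulated trials per scenario, shown for 9.9 / 13.5 patients per month. The delay runs from the crossing to patient 100 and supposes that nobody acts sooner.

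| Assumed risk | Count | Chance before patient 100 | Mean delay (months) | Further patients entered |
|---|---|---|---|---|
| Attempt 3% | 6 | 1.3 / 0.5% | 1.13 / 0.62 | 11.7 / 8.9 |
| Attempt 6% | 6 | 19.2 / 9.4% | 1.43 / 0.81 | 14.7 / 11.5 |
| Attempt 12% | 6 | 80.2 / 60.6% | 2.32 / 1.23 | 23.5 / 17.2 |
| Suicide 1.5% | 3 | 7.5 / 4.5% | 1.91 / 1.20 | 19.4 / 16.6 |
| Suicide 3% | 3 | 30.7 / 20.7% | 2.22 / 1.36 | 22.4 / 18.9 |
| Suicide 6% | 3 | 75.6 / 61.2% | 2.93 / 1.75 | 29.5 / 24.2 |

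**Hand check at the alarm level.** When patient 100 enters, patient *i* has completed the fraction min(1, (100 − *i*)/(7 × rate)) of the 7 months.
- At 9.9 per month, 7 × 9.9 = 69.3 and the fractions sum to 30 + 2415/69.3 = 64.8. Expected attempters: 0.06 × 64.8 = 3.89. Expected suicides: 0.03 × 64.8 = 1.95.
- At 13.5 per month, 7 × 13.5 = 94.5 and the sum is 5 + 4465/94.5 = 52.2. Expected attempters: 3.13. Expected suicides: 1.57.
- Poisson tails for at least 6 attempters: 19.8% and 9.8%. For at least 3 suicides: 30.9% and 20.8%. These agree with the simulation.

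**Overlap with the first scheduled DMC meeting.** At the alarm level, the median early crossing falls at month 8.9 / 6.8 (attempts) or 8.1 / 6.3 (suicides). Only 2 / 18% and 13 / 40% of the early crossings come before month 6, the earliest date of the first meeting after start-up.

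**If *enrolled* means consented.** 100 consented corresponds to 100 × 360/800 = 45 up to 100 × 360/720 = 50 randomised. The chance at the alarm level is then at most about 0.06% (attempts) and 1.6% (suicides). In the worst scenario in the table it is about 9%.

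**Effect of the definition at full enrolment.** With 360 randomised: 3% gives 10.8, so 11 suicides; 6% gives 21.6, so 22 attempters. With 720–800 consented: 22–24 suicides or 44–48 attempters.

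**The case against.** The rule is coherent as it stands: a percentage trigger with a minimum denominator is an ordinary choice, and it need not mirror the seizure rule. The early period is also well covered. Beyond the provisions listed above, section VI.H.3 has the pharmacy coordinating centre evaluate every SAE and confer with the study chair as needed, and VI.H.4 lets the DMC set its own schedule for safety summaries. X.B.8 sends every suicide and attempt to the executive committee, the Central IRB and the DMC. Recent attempters are excluded, suicidality scales are given weekly during acute treatment, and safety plans are required. The DMC guidelines set before start-up are not shown and may already contain an earlier trigger.

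Most of this stands, and it limits the point. A reader might infer that suicide goes unmonitored before patient 100; the documents do not support that. What remains is narrower: in the protocol as shown, every route to an early pause in enrolment is discretionary, and the patient-level measures do not suspend enrolment.

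A reader might also take the rule to be first checked at patient 101, where 3/101 = 2.97% and 6/101 = 5.94% miss and 4 or 7 would be needed. That reading is strained. The ordinary sense is that the rule runs once 100 patients are in, and nothing here rests on the other.

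**Conclusion.** The point holds as a cheap improvement of modest size. The automatic trigger is silent in exactly the situation where the sponsor's own counts would be most alarming, and until patient 100 a pause depends on discretion.

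The size rests on assumed risks, even timing of events and *enrolled* meaning randomised. At the rule's own risk levels the early crossing is a minority event and costs about 1–2 months on average. Across all assumed scenarios the mean delay is 0.6–2.9 months, and each figure is an upper bound in that it supposes no body acts on several reported SAEs. The probability becomes high only if true risk is about twice the alarm level. The case for changing the text is the low cost of the change, not a large expected effect.

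**What to change.** In X.B.8, state that enrolment is suspended pending DMC review as soon as 3 participants have a completed suicide or 6 different participants have attempted suicide, at any time up to and including the 100th randomised patient. After that, it is suspended when the proportion is at least 3% or at least 6% of those randomised. Add that, once the DMC has cleared a pause, the trigger applies again only on a further event at or above the threshold, or at a new threshold set by the DMC. Without this, cumulative counts could stop enrolment again on events already reviewed.

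Define *enrolled* as randomised for this rule. That matches the Executive Summary, section VI.C and Appendix D, and removes the conflict with VI.A.3.

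The cost is two or three sentences. No new data or staff are needed, because the events are already reported as SAEs. The downside is an occasional earlier temporary pause and possibly a second review around patient 100. In the alarm-level simulations the count was still exactly 6 at patient 101 in 49 / 57% of early crossings, and still exactly 3 in 56 / 63%, so a further event had occurred by then in the remaining 37–51%.

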APPENDIX A

HUMAN RIGHTS ISSUES

HUMAN RIGHTS COMMITTEE MINUTES and INFORMED CONSENT FORMS

HRC Minutes dated 08/11/2005

HRC Minutes dated 09/16/2005

HRC Minutes dated 09/28/2005

HRC Minutes dated 03/20/2007

HRC Minutes dated 05/15/2007

HRC Minutes dated 03/19/2009

A Comment on Informed Consent

It is the responsibility of study staff to protect veterans and ensure that their participation is based upon an sufficient understanding of the study. Thus, informed consent is one of the pillars of ethical human subjects research. Study staff are obligated to work with veterans so that they have the opportunity to make an informed decision as to whether or not to participate in research. A key component in the informed consent process is the dialogue between the study staff and the veteran.

As an additional safeguard to ensure that all participants are making an informed decision is the inclusion of a quiz at the conclusion of the informed consent document. This **Attachment** item, true/false quiz addresses major points from the informed consent document and serves as a point of discussion between study staff and the veteran. Should a veteran answer any of the items incorrectly, study staff must use this opportunity to more fully discuss that information from the informed consent with the veteran. This discussion should continue until study staff are satisfied that the veteran is clear on the issue at hand. Thus this is not a pass/fail test and no data will be collected from this document.

There may be instances when study staff question a “consent capacity.” Should this occur, study staff are to follow their local VAs guidelines for the assessment of capacity to consent to participate in research. If the local VA does not have such guidelines, study staff will receive guidance from the Chairman’s Office as to how to proceed with

such an evaluation. Key components of consent capacity assessment including components of the research such as the study purpose, experimental components, associated risks and benefits, voluntary nature of participation and alternatives to participation. The determination of whether a prospective subject is capable of providing informed consent is based on a consideration of relevant study factors and an individual's consent capacity.

**COOPERATIVE STUDIES PROGRAM COORDINATING CENTER
PERRY POINT, MARYLAND
HUMAN RIGHTS COMMITTEE MEETING
Sheraton BWI ([name])
August 11, 2005**

A meeting of the Human Rights Committee occurred on August 11, 2005 with the following in attendance:

[name]., M.S.
[name]
[name]
[name]., J.D.
[name].
[name].

ABSENT:

[name]., M.P.H.
[name]., M.S.
[name], J.D.
[name]

Non-Committee members:
CSPCC: [name], Sc.D.
[name]
[name]
[name]
[name]
[name], M.S.

Study Representatives (Palo Alto VA):
[name].
[name].

The committee met for the initial review of the protocol and informed consent for CS #556, "The Effectiveness of rTMS in Depressed VA Patients" which will be submitted to the CSSMRB in November 2005.

The following materials were provided to the committee:

- Protocol (included the following documents):
 - Executive Summary (Abstract) – pages 3-4
 - Informed Consent Materials (Version 2.0, dated August 9, 2005)
- Consent Form Checklist

[name] gave an overview of the study to the committee. The purpose of this study is to evaluate the efficacy, safety, durability of benefits and cost-effectiveness of repetitive Transcranial Magnetic Stimulation (rTMS) in the resolution of treatment-resistant major depression (TRMD). Two hundred and forty veterans diagnosed with TRMD will be enrolled at 8 VA Medical Centers over a 2 ½ year period. Participants will be randomized into a double blind clinical trial to left prefrontal rTMS treatment or to sham (control) rTMS treatment for up to 30 treatment sessions. The primary outcome measure is to assess the efficacy of rTMS in veterans to bring about remission of TRMD.

The committee members reviewed both the protocol and informed consent and formulated a list of recommendations/concerns. The study Chairman, [name], and [name] were then asked to join to committee meeting. [name] provided a concise summary of the study indicating that the major risk of the study was the possibility of seizures. Other side effects include tension headaches and/or the possibility of hearing loss. He also informed the committee that the sham will deliver the same noise as the active rTMS coil, but that neither would produce warmth or the possibility of a burn. Both [name] and [name] fielded questions from the committee members. They were:

- Safety (Risk of Seizures): The protocol states that 8 seizures have been reported secondary to rTMS. The committee requested information regarding the overall numbers of individuals treated. [name] indicated that the literature does not provide firm numbers, but his estimate would be upwards around 100,000.

- Genetics Subprotocol: There is very little information in the protocol regarding this portion of the study. [name] indicated that all genetics subprotocols are handled by the Palo Alto Coordinating Center and once it is received at Perry Point it will be presented to the Human Rights Committee to review. There will be a separate informed consent for this subprotocol.

- Depression Rating Scale: The committee suggested that a patient depression rating scale be included in this study. [name] agreed that this could be done.

- Independent Assessment of Subjects. The committee expressed concern about the ability of severely depressed subjects being able to comprehend and sign an informed consent. [name] indicated that the protocol will be revised to state that if the physician feels that the subject may not be capable of understanding the protocol or informed consent that an independent assessment of the subject will be requested.

The committee suggested the following changes be made to the informed consent.

General

1. Lower reading level of informed consent.
2. Remove the term “non-invasive” throughout informed consent.
3. Authoritative language throughout informed consent should be softened. In other words, phrases such as “you will be required” should be changed to “you will provide.”
4. The term “feelings of suicide” which is used throughout informed consent should be changed to read “thoughts or feelings of suicide.”

Specific

Page 1 (Terms Section)

- Under rTMS. The sentence reads, “A repetitive Transcranial Magnetic Stimulation machine is an experimental device that is capable of delivering a higher number of stimuli per second.” Change the word “higher” to “high”.

Page 2 (Purpose and Background of the Study)

- The last sentence of the last paragraph, “Your duration in the study will last 11 to 21 weeks.” needs to be further explained. Perhaps the sentence could read, “Your participation in the study will be a maximum of 21 weeks.”

Page 3 (Screening Phase)

- Fifth bullet from end. Last sentence of that paragraph should be inserted after first sentence.

Page 3 (Acute Treatment Phase)

- Last sentence of first paragraph reads, "The final treatment session may occur after 15, 20, 25 or 30 sessions and will require approximately 3 hours of your time." An explanation needs to be included as to "why" the final treatment sessions may occur at any of these time intervals. Perhaps it should read, "At the end of the 15th session you will be evaluated to determine the need for future sessions."

Page 4 (Description of Study Treatment)

- Last sentence of first bullet reads, "Your head will be placed in a rigid holder so that the rTMS coil is correctly positioned on your head." It should be changed to read, "Your head will be placed in a **fixed (or stationary)** holder...."

Page 5 (Description of Study Treatment)

- Last bullet. Take out reference to the 3,200 pulses.

Page 5 (Follow-Up Phase)

- 3rd bullet. This information says that the subject will be asked about any suicidal feelings at follow-up week 6. The committee suggested that this occur throughout the study. [name] indicated that this would be added to the protocol.

- Last bullet. Change last bullet to read as follows: "At your final follow-up visit, you will be asked whether you believe you received the active treatment or the sham (inactive) treatment."

Page 7 (Potential Risks and Discomforts)

General Comment for this section: The committee suggested that more detail than necessary is provided in this section. It is recommended that many of the details can be removed and the section should clearly list the possible risks.

- 3rd bullet: This bullet should concentrate on why there is a potential for hearing loss and why the subject should wear earphones. The information regarding "minor burns" should be removed since the coil technology has changed and there is no risk for burns. The description of the sound under this bullet (light tapping sound) is inconsistent with the description of the sound as presented in bullet # 8.

- 4th bullet: The sentence reading, "rTMS is frequently uncomfortable for patients because the magnetic pulses cause facial and scalp muscles to contract." should be combined with bullet # 9. A comment should be made that the feelings of numbness in the face are temporary.

- 5th bullet: The following two sentences under this bullet contradict one another:
“Since that time, there have been two reports of what may have been seizures.”
“There have been no treatment-related seizures reported in current ongoing clinical trials.”
Also, the term “treatment-related” needs to be defined.

Page 8 (Potential Risks and Discomforts)

- 3rd bullet from end. Take out the reference to the study assessments being “frustrating and time-consuming.”

Page 8 (Pregnancy)

- Combine this section with the “For Women Only” section.

Page 8 (Anticipated Benefits of the Study)

- Include any known benefits of rTMS.

Page 9 (Withdrawal From the Study)

- Last bullet. Last portion of sentence should read, “...might influence your willingness to continue participating.”

RECOMMENDATION: The committee suggested that the recommendations be incorporated into a revised protocol and informed consent and presented to the committee for final approval at its next meeting.

[name].
Acting Chairperson, Human Rights Committee

Department of Veterans Affairs

Memorandum

Date: September 16, 2005

From: Director, Cooperative Studies Program
Coordinating Center, [name] 21902

Subj: Response – CSP #556, “The Effectiveness of rTMS in Depressed VA Patients”

To: Human Rights Committee Members

1. On August 11, 2005, the Human Rights Committee (HRC) met to review CSP #556, “The Effectiveness of rTMS in Depressed VA Patients”.

Following this review, your committee identified several areas in the **STUDY PROTOCOL** that required further clarification. Below is a brief description of each issue and the corrective action taken:

a. **Recommendation:** Clarify the risk of seizures.

Corrective Action: “The risk of seizures for rTMS treatment is less than 1%” (page 15 of revised protocol).

b. **Recommendation:** In addition to the Beck Scale for Suicidal Ideation (BSS), include a self-administered depression rating scale in the protocol that will be conducted at screening and on a weekly basis.

Corrective Action: The Beck Depression Inventory (BDI) has been added as a secondary outcome measurement tool. Both the BDI and the BSS are self-administered assessment tools that will be conducted at screening, during sessions 1 through the end of the final acute treatment phase and during follow-up weeks 1 through 6 (pages 23, 32 and 35 of revised protocol).

c. **Recommendation:** Clarify if there is a need for an independent assessment of a severely depressed patient’s ability to comprehend and sign an informed consent.

Corrective Action: “If the SI feels that the patient may not be capable of giving informed consent, the SI may request a competency evaluation” (page 27 of the revised protocol).

The changes cited above have been incorporated into the revised protocol (dated September 16, 2005) and references have been consistently integrated throughout the document.

2. Your committee also identified several significant issues with the **INFORMED CONSENT**. After carefully reviewing your recommendations, the following corrective actions were initiated:

- a. The definition of the rTMS machine has been revised to say: "A repetitive Transcranial Magnetic Stimulation machine is an experimental device that is capable of delivering a high number of magnetic pulses per second" (page 1 of the revised consent).
- b. Clarified the participant's duration in the study to be a maximum of 21 weeks (page 2 of the revised consent).
- c. Clarified the description of the Acute Treatment Phase to read: "Each treatment session will last approximately one hour of which 38 minutes will consist of the actual rTMS treatment. After every fifth treatment, you will meet with a member of the study staff to complete various study assessments that will last up to an additional hour. After the 15th session, you will be evaluated to determine if there has been any improvement in your symptoms of depression. This evaluation will determine if any future sessions are needed. Your final treatment session will require approximately 3 hours of your time" (page 3 of the revised consent).
- d. Replaced the term "feelings of suicide" with "thoughts or feelings of suicide" throughout the document.
- e. Added an additional self-assessment for depression that will be conducted throughout the study (pages 4 and 5 of the revised consent).
- f. Edited the Potential Risks and Discomforts section for organization, content and terminology. Side effects of hearing loss, headaches, muscle twitching, temporary numbness in the face and seizures have been clarified (page 6 of the revised consent).
- g. Various sections throughout the document have been thoroughly reorganized and edited. The language has been softened and, whenever possible, technical passages have been replaced with layman's terms. Per the Lix Readability Scale, this document is rated at an 8th grade reading level.
- h. Enhanced the "Anticipated Benefits of the Study" section to reflect the potential QOL benefits and the greater accessibility of this treatment to our veterans (page 7 of the revised consent).

3. Please note that since the August 11th HRC meeting, several **MODIFICATIONS** have been made to the CSP #556 protocol. The changes are as follows:

- A TSH, T₃ and T₄ have been added to the laboratory studies performed at screening (see page 33 of the revised protocol).
- An electrocardiogram (ECG) will be performed at screening (pages 32 and 33 of the revised protocol and page 3 of the revised consent).

- A short videotape of an actual rTMS treatment will be provided to each site for the patients to view (page 1 of the revised consent).
- The "review of medication use" has been expanded to include "natural food products" (page 33 of the revised protocol and page 2 of the revised consent).
- A brief description of scalp electrodes has been added to the "Description of Study Treatment" (page 4 of the revised consent).
- A section has been added to the "Use of Research Results" section for the patient to agree to the use of their social security number to access VA and HCFA databases (pages 8 and 9 of the revised consent).
- With the addition of the BDI as a self-administered assessment for depression, the HUI will no longer be required and has been deleted from the protocol. Also, the "Economic Issues" and the "Economic Analysis" sections of the protocol have been expanded (pages 20, 49 and 50 of the revised protocol).

[figure not shown]
I am enclosing a copy of the revised protocol and the informed consent with the above cited changes highlighted in YELLOW. Also enclosed is a copy of the Human Rights Committee minutes for the August 11th meeting that itemizes your recommended changes.

As you can see, the CSP #556 study team has very carefully reviewed your comments/recommendations and has initiated appropriate corrective actions. The team remains very committed to this research study and will make every effort to ensure that it is a success.

If you feel that the human rights issues have been satisfactorily resolved, please indicate your approval below. You may contact me if you have any questions or concerns that you would like to discuss. I can be reached at [contact], [name].

We appreciate your time in reviewing these revised documents and we look forward to the results of your second review.

Sincerely,

[name], Sc.D.
Director, Cooperative Studies
Program Coordinating Center
Perry Point, Maryland 21902

APPROVE:	Date
[name]., MPH Chairman, Human Rights Committee	

Enclosures (5) Study Abstract
